5.2.1 Baseline (all parameters except ALSFRS-R)

Baseline is defined as the last available value before or on the same day as first treatment intake, i.e. value at inclusion (V0) or value at screening visit if no value is available at inclusion.

5.2.2 ALSFRS-R Baseline

ALSFRS-R baseline is defined as

- The screening value OR
- The V0 value if V0 is performed > 15 days after the screening visit and available before or on the same day of first treatment intake

STATISTICAL ANALYSIS PLAN		
InFlectis BioScience	Sponsor:	InFlectis BioScience
	Protocol Number:	P288ALS
VERSION 1.0 NOV 12, 2024		

If ALSFRS-R was evaluated at V0 while V0 was performed 15 days or less than 15 days after screening, the value at screening will be considered as baseline value.

5.2.3 Change from Baseline

Absolute change from baseline for any variable at a given visit will be calculated by subtracting the baseline value of that variable from the value of the variable at the given visit, eg for Visit 4 at month 6:

$$\text{Change from baseline to month 6} = \text{month 6 value} - \text{baseline value}$$

If there is no baseline value, then the absolute change from baseline will be set to missing.

5.2.4 Relative change from Baseline

Percent relative change from baseline for continuous variables at a given visit will be calculated by subtracting the baseline value of that variable from the value of the variable at the given visit and then dividing by the baseline value, all multiplied by 100 e.g. for month 6:

$$\text{Relative change from baseline to month 6} = 100 * (\text{month 6 value} - \text{baseline value}) / \text{baseline value}$$

If there is no baseline value, then the relative change from baseline will be set to missing.

5.2.5 Study visit

If a premature discontinuation visit occurs between [83-99] days after V0 then consider this visit as V3 visit.

If a premature discontinuation visit occurs between [170-194] days after V0 then consider this visit as V4 visit.

5.2.6 Conventions for Missing and Partial Dates

Imputation rules for missing start date of treatment:

- If start date of treatment, defined as study first drug intake corresponding to the date of the baseline (V0) visit, is missing the date of randomization is taken.

Imputation rules for partial or missing start dates for AE/medication:

- If the month and year are present, impute the day by the first of that month.
- If the month and year are the same as those of the date of first dose, impute the day with the day of first intake of treatment.

STATISTICAL ANALYSIS PLAN		
InFlectis BioScience	Sponsor: Protocol Number:	InFlectis BioScience P288ALS
VERSION 1.0 NOV 12, 2024		

- If only the year is present, impute by January 1st of that year.
- If the year is the same as the year of the date of first dose, impute by the day of first intake of treatment.
- If the start date is entirely missing, impute by the day of first intake of treatment.
- If after imputation AE/medication start date is posterior to AE/medication end date, then imputed start date should be replaced by AE/medication end date.

Imputation rules for partial or missing stop dates for AE and medication:

- If the month and year are present, impute the day by the last day of that month.
- If only the year is present, impute by December 31st of that year.
- If the stop date is entirely missing, assume the event or medication is ongoing except if patient is dead impute by the date of death

Imputation rules for partial date of ALS diagnosis/ date of first signs/symptoms:

- If the month and year are present, impute the day by the 1st of that month.

5.2.7 Completion of visits

A visit will be considered as having been completed if a visit date is reported for this visit.

5.2.8 Treatment status

The treatment status will be considered as:

- “Completed” if the patient has completed the V4 visit without having permanently stopped the treatment before the V4 visit.
- “Discontinued” if the patient has permanently discontinued the treatment before the V4 visit.

5.2.9 Study status

The study status will be considered as:

- “Completed” if the box “Yes” for the question “Was the study completed?” in the End of Study form of the eCRF is ticked.
- “Discontinued” if the box “No” for the question “Was the study completed?” in the End of Study form of the eCRF is ticked.

5.2.10 Last IMP intake

STATISTICAL ANALYSIS PLAN		
InFlectis BioScience	Sponsor:	InFlectis BioScience
	Protocol Number:	P288ALS
VERSION 1.0 NOV 12, 2024		

Date of last IMP intake will be the date of V4 for patients with “treatment status” at “completed”.

Date of last IMP intake will be end of study date for patients with “treatment status” as “discontinued”.

5.2.11 Treatment duration

The duration of treatment (days) will be derived as follows: (Date of last visit on treatment administration – date of last IMP intake + 1).

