4.1.9 Premature discontinuation visit

Patients who prematurely withdraw from the study for any reason (Section 5.3), should be scheduled for a final visit as soon as possible and no later than 4 weeks after the last IMP intake.

The following assessments will be conducted:

- Physical examination and vital signs assessment, according to [Sections 4.2.1.2](#) and [4.2.1.5](#),
- Weight and calculation of BMI,
- 12-lead ECG ([Section 4.2.1.6](#)),
- Blood and urine sample collection for haematology, blood chemistry, and urinary analysis according to [Section 4.2.1.8](#),
- Crystalluria analyses according to [Section 4.2.1.9](#),
- Query for changes in concomitant medications,
- Recording of AEs (if any),
- ALSFRS-R measurement,
- ALS-MITOS measurement,
- King's College score measurement,
- Bioelectrical Impedance Analysis,
- C-SSRS evaluation,
- Patient's completion of ALSAQ-40,
- SVC assessment,
- Urine pregnancy test in WOCBP,
- Sniff test⁹,
- ABG,
- International Normalized Ratio (INR) if CSF sampling is planned,
- Collection of blood, urine and CSF samples for biomarkers analysis according to [Section 4.2.2.3](#),
- eCRF recording of data collected.

⁹ The sniff test is optional. It will be performed only in sites that have the equipment and resources to perform this test.

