6.1.2 Administration of the investigational medicinal products

Only patients enrolled in the study will receive the study products and only trained and authorised site staff will handle and supply them. Patients will receive the IMPs kit directly from the investigator or the medicine will be sent directly to the patient from the site pharmacy.

The patients will receive the IMP at baseline visit (V0: 2 bottles), V2 (2 bottles) and V3 (2 bottles) visits. They will be instructed to take the IMP orally twice a day (morning and evening uptakes). Intervals for dosing should ideally be about 12 hours (\pm 1 hour). Tablets shall be swallowed with a glass of water 30 minutes before the meal, in fasting condition. For patients who have swallowing difficulties, tablets can be taken in a spoon filled with jellified water. IFB-088 and riluzole will be taken at the same time. Dosage modifications are not permitted. However, in case of unplanned dosage modification by the patient, it shall be documented in the eCRF. Missed doses will not be made up for. In case of vomiting shortly after ingestion of the study product, the patient will leave out the potential missed dose and will take the next dose as normal. Study product doses withheld due to toxicities and AEs will not be made up later. Should the patient or the investigator wish to discontinue treatment for any reason, they may do so at any time. The date of the last uptake will be documented in the eCRF.

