5.2.12 Study duration

The duration of study (days) will be derived as follows: (End of study date – date of screening visit +1).

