5.2.14 Compliance

Compliance will only be assessed for patient present at V4 over the treatment period until V4 and defined as:

(Number of pills taken / Number of theoretical pills to be taken) * 100

Total number of pills dispensed = Total number of dispensed bottles (sum of all bottles dispensed during the study) * 65

Number of pills taken = total number of pills dispensed - number of remaining pills at V4

Number of theoretical pills to be taken = Date of V4 – Date of V0 (in days) * 2

Compliance (Yes/No): a global compliance higher than 80% is considered as a good compliance.

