5.4 Patient Disposition

Subject disposition will be summarized as follows:

- The number of patients who failed screening and the reasons for failure will be tabulated for the Screened Set.
- The number of patients who were screened, randomized, treated, randomized or treated (i.e. enrolled) and who are in each analysis set will be summarized by treatment group and overall for the Screened set.
- The number of patients completing the study and those prematurely discontinuing the study as well as the reasons for discontinuation will be tabulated by treatment group and overall.
- The number of patients present at each scheduled visit will be summarized by treatment group.
- The reasons for exclusion from the PPS will be summarized by treatment group and overall.
- Study duration (days) will be summarized by treatment group and overall in RS.
- Treatment duration (days) will be summarized by treatment group and overall in RS.

Early termination (ET) assessments as well as V3 bis will only be listed and not included in by-visit summary displays.

All patients disposition data will also be listed.

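### SAP 5.2.11 computes treatment duration from two end dates and no start date, and SAP 5.2.10 replaces the recorded last dose of early stoppers with their end-of-study date

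*SAP*

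**What the plan says.** SAP 5.2.11 gives treatment duration in days as "Date of last visit on treatment administration – date of last IMP intake + 1".

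SAP 5.2.10 supplies the last-intake date. For patients whose treatment status is completed it is the V4 date. For the others, "Date of last IMP intake will be end of study date for patients with" a discontinued treatment status. SAP 5.2.8 counts a patient as completed if V4 was done and treatment had not been permanently stopped before it.

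The SAP does hold a start date. In SAP 5.2.6 the start of treatment is "defined as study first drug intake corresponding to the date of the baseline (V0) visit". The formula that follows, study duration in SAP 5.2.12, has the usual end-minus-start form: "End of study date – date of screening visit +1".

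The actual last dose is also meant to be on record. Protocol 6.1.2 states: "The date of the last uptake will be documented in the eCRF". Under Protocol 4.1.9, patients who withdraw early "should be scheduled for a final visit as soon as possible and no later than 4 weeks after the last IMP intake".

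The derived variable is reported in SAP 5.4: "Treatment duration (days) will be summarized by treatment group and overall in RS".

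**The concern.** There are two separate errors.

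The first is that the formula measures the distance between two markers of the end of treatment. It cannot return time on drug, whatever dates are put in. The neighbouring study-duration formula is built correctly, so this looks like a drafting slip for the date of first intake.

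The second is that SAP 5.2.10 replaces a recorded last dose with a later proxy for exactly those patients whose treatment was shorter than planned. The end-of-study date cannot normally precede the last dose, so the error runs only upwards.

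The second error is the more troublesome. A column of 1s would be noticed at programming. Inflated but plausible durations for early stoppers would not. Compliance does not fill the gap, because "Compliance will only be assessed for patient present at V4 over the treatment period until V4". For patients who stop before V4, the duration row is therefore the only planned summary of days on drug, in a trial whose primary objective is safety.

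**Working it through.** **Planned period.** Count days from V0 = 0, with the intervals in Protocol 3.1: V2 at 4 weeks, V3 9 weeks after V2, V4 13 weeks after V3. Then V4 = 4 + 9 + 13 = 26 weeks = day 182, which reproduces the stated 26-week treatment period.

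**Completer, SAP as written.** Last intake = V4 (SAP 5.2.10). The last visit on treatment is not defined, but SAP 5.2.8 makes V4 the natural reading.

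- Duration = 182 − 182 + 1 = **1 day**, whatever the actual V4 date.
- If the phrase meant the last dispensing visit (V3, day 91): 91 − 182 + 1 = −90.
- If it meant the last on-site dosing visit (V2, day 28): 28 − 182 + 1 = −153.

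No reading gives about 183.

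**Completer, with a start date.** Last intake − first intake + 1 = 182 − 0 + 1 = **183 days**. With V4 at week 26 ± 4 days (Protocol Table 2), V4 falls on day 178 to 186 and the duration is 179 to 187. If the ±4-day windows at V2, V3 and V4 are chained as in Protocol 3.1, V4 falls on day 170 to 194 and the duration is 171 to 195.

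**Early stopper, SAP as written.** The end-of-study date is never earlier than the last on-treatment visit, so the result is at most 1 day. It is 0 or negative whenever end of study is later. Example, assuming a last dose on day 60, V2 as the last on-treatment visit (day 28) and end of study 0 to 28 days after the last dose: 28 − 60 + 1 = −31 down to 28 − 88 + 1 = −59, against a true 61.

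**Early stopper, subtraction repaired but SAP 5.2.10 unchanged.** Let d be the day of the last dose and g the gap to end of study. True duration = d + 1; derived duration = d + g + 1. Assume the discontinuation visit marks end of study, so g = 0 to 28 (the 4-week limit in Protocol 4.1.9).

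| Last dose (day) | True | Derived | Largest overstatement |
|---|---|---|---|
| 30 | 31 | 31 to 59 | 28/31 = 90% |
| 60 | 61 | 61 to 89 | 28/61 = 46% |
| 120 | 121 | 121 to 149 | 28/121 = 23% |

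**Corner case.** After emergency unblinding, Protocol 3.9.1.1 stops the drug but encourages the patient to keep attending scheduled visits. If such a patient took the last dose on day 60 and end of study is the follow-up visit (week 30 ± 1 week, day 203 to 217), the derived duration is 210 − 0 + 1 = 211 (204 to 218) against a true 61. That is longer than a completer's 183.

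**The case against.** The strongest case is about weight. The variable feeds one descriptive row. The TEAE definition (SAP 5.2.15), the compliance formula (SAP 5.2.14) and the efficacy models do not use it. The 1-day result would reveal itself. The substitution touches only early stoppers, roughly 7 or 8 patients at the planned 15% drop-out among 50 (0.15 × 50 = 7.5). All of this stands and limits the scope, but it does not make either rule correct.

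Four narrower objections:

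- The 1-day value depends on reading an undefined phrase as V4. True, but the alternatives give negative numbers.
- The 179 to 187 range uses only the Table 2 window. The chained windows of Protocol 3.1, which match the day 170 to 194 range in SAP 5.2.5, widen it to 171 to 195. The conclusion is unaffected. Protocol 3.7 also asks that a shifted visit should not shift the next, which supports the narrower range.
- The 211-day case is rare. Protocol 5.3 withdraws patients after more than 10 days off drug and collects no further data on withdrawn patients beyond the discontinuation visit. The 0-to-28-day range is the one to rely on, and 28 is the protocol's limit, not the expected gap.
- SAP 5.4 plans other disposition output: attendance by visit, reasons for discontinuation, study duration and listings. None of these summarises days on drug.

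The eCRF itself is not among the documents, so the completeness of the last-dose field cannot be confirmed. That is a reason to keep a fallback rule.

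**Conclusion.** Both errors hold. As written, SAP 5.2.11 gives completers 1 day instead of about 183, and no interpretation of its terms repairs it. SAP 5.2.10 separately overstates early stoppers' time on drug. The overstatement is zero if last dose and end of study coincide, up to 28 days if an on-time discontinuation visit closes the study, and more only if follow-up continues off drug. These sizes rest on assumed scenarios, because the SAP does not define the end-of-study date for an individual patient.

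The consequence is a wrong by-arm treatment-duration summary in SAP 5.4. No primary-endpoint or inferential result changes. The changes listed in SAP section 7 do not address it. It should be fixed before the analysis is programmed, and both sections should be corrected together, since repairing the subtraction alone would leave the less visible error in place.

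**What to change.** - **SAP 5.2.11:** treatment duration = date of last IMP intake − date of first IMP intake (V0) + 1.
- **SAP 5.2.10:** for patients with discontinued treatment, take the last-uptake date recorded in the eCRF. Use the end-of-study date only when that date is missing, and flag those patients in the listing.

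The cost is two lines of SAP text. SAP 5.2.6 already defines the first-intake date and Protocol 6.1.2 already requires the last-uptake date to be recorded, so no new data are needed.

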5.2.12 Study duration

The duration of study (days) will be derived as follows: (End of study date – date of screening visit +1).

5.2.13 Amyotrophic lateral sclerosis history

Time from ALS diagnosis to screening (in months) will be derived as: (date of screening visit – date of ALS diagnosis + 1)/30,4375.

Time from onset date of first ALS symptoms to screening (in months) will be derived as: (date of screening visit – date of onset of first ALS symptoms + 1)/30,4375.

5.2.14 Compliance

Compliance will only be assessed for patient present at V4 over the treatment period until V4 and defined as:

(Number of pills taken / Number of theoretical pills to be taken) * 100

Total number of pills dispensed = Total number of dispensed bottles (sum of all bottles dispensed during the study) * 65

Number of pills taken = total number of pills dispensed - number of remaining pills at V4

Number of theoretical pills to be taken = Date of V4 – Date of V0 (in days) * 2

Compliance (Yes/No): a global compliance higher than 80% is considered as a good compliance.

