3.7 SCHEDULE OF ACTIVITIES

The scheduling of study procedures is outlined in [Table 2](#) and detailed in [Section 4.1](#).

All data obtained from the assessments listed in the schedule of activities and described in detail in [Section 4.2](#) must be supported in the patient's source documentation (e.g. medical charts or patient notes).

Visit dates should be adhered to as closely as possible. If one visit is postponed or brought forward, it should not result in the next visit being postponed or brought forward. The next visit, if at all possible, should adhere to the original time schedule.

Table 2 – Schedule of activities

Visits	Screening	Baseline V0	V1	V2	V3	V3bis	V4	Premature discontinuation	V-FU
Study Weeks	Within 2 weeks before V0	0	2 ± 3 days	4 ± 4 days	13 ± 4 days	19.5 ± 4 days	26 ± 4 days	-	30 ± 1 week
Informed consent ⁽¹⁾	X								
Inclusion/exclusion criteria	X	X							
Demographic characteristics	X								
Medical history	X								
Physical examination and vital signs	X	X	X	X	X	X ^x	X	X	X
Weight / BMI	X	X	X	X	X		X	X	X
ECG	X	X*		X	X	X	X	X	X
Serum/urine chemistry	X	X*†	X	X††	X†††	X ^y	X	X	X
Serum pregnancy test	X								X
Urine pregnancy test ^f		X		X	X		X	X	
Neuropsychological assessment	X								
Concomitant medications and AEs	X	X	X	X	X	X	X	X	X
Crystalluria examination				X				X	X
Randomisation		X							
Study drug delivery		X ^a		X	X				
ALSFRS-R	X	X**			X		X	X	
ALS-MITOS		X			X		X	X	
King's College		X			X		X	X	
C-SSRS evaluation ⁽⁴⁾	X				X		X	X	
Bioelectrical Impedance Analysis		X			X		X	X	
ALSAQ-40		X					X	X	
SVC	X				X		X	X	
Sniff test ⁽²⁾	X				X		X	X	
ABG	X				X		X	X	
Plasma biomarkers		X			X		X	X	

Whole blood biomarkers		X					X	X	
Urine biomarkers		X					X	X	
International Normalized Ratio ^{ff}		X				X ^z	X	X	
CSF sampling ^{fff}		X					X	X	
Blood samples for PK				X					
Administration of study drug on site				X ⁽³⁾					

*Will be performed only if deemed necessary by the investigator.

^f In addition to tests mentioned in the table, pregnancy tests will be performed at monthly intervals during treatment and until the end of relevant systemic exposure.

^{ff} Will be performed only if V0 is performed > 15 days after the screening visit.

[†] A **prescription** will be given to patients at V0 to perform urine analysis and blood sampling in a local laboratory at V0 + one week.

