 - Study product must be taken at approximately the same time each morning and each evening, about 12 hours apart, with a glass of water and 30 minutes before the meal, in fasting condition. For patients who have swallowing difficulties, tablets can be taken with a spoon filled with jellified water. The patient will take the first tablet at the V0 visit under a healthcare professional supervision. If this first intake is in the morning, the patient will take his next dose in the evening at home. If the first intake is in the afternoon, the patient will take the next dose at home the next morning. From the second intake, intervals for dosing should ideally be about 12 hours (\pm 1 hour).
 - Study drug must be kept in the original container, at room temperature,
 - Daily dose of riluzole must be taken at approximately the same time each morning and each evening, together with the study product,
 - Both used and unused study drug bottles must be returned at the next visit for treatment accountability,
 - The patient will be encouraged to stay well hydrated throughout the duration of the study.
- ALSFRS-R measurement if V0 is performed $>$ 15 days after screening visit,
- ALS-MITOS measurement,
- King's College score measurement,
- Bioelectrical Impedance Analysis
- Patient's completion of ALSAQ-40,
- International Normalized Ratio (INR) if CSF sampling is planned,
- Collection of blood, urine and CSF samples for biomarkers analysis according to [Section 4.2.2.3](#),

- Appointment for the next visit,
- eCRF recording of data collected.

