6.1.3 Supply and storage conditions of the investigational medicinal products

IFB-088 and placebo supplied by the sponsor to be used in this study will be manufactured, tested, handled and stored according to current Good Manufacturing Practice (GMP) requirements for clinical trials.

The sponsor will provide the study centre with the test product and the placebo. The investigator or pharmacist (if applicable) will receive numbered products. The investigator/pharmacist is responsible for a safe and proper handling and storage of the study drug at the investigational site. The study drug must be stored in a locked facility with restricted access to the investigator/pharmacist and authorised personnel. The study products have to be stored at room

temperature. The investigator or designee must confirm appropriate temperature conditions have been maintained during transit for each study product received.

The investigator and/or a pharmacist or another appropriately trained individual is obliged to document the receipt, dispensation, and return of all study products received during this study.

Records on receipt, use, return, loss, or other disposition of study drugs must be maintained. The investigator and/or a pharmacist or another appropriately trained individual must sign the receipt forms. Records on study drug delivery to the site, the inventory at the site, the use by each patient, and the return to the sponsor must be maintained by the investigator and/or a pharmacist or another appropriately trained individual at the investigational site. Patients will be asked to return all unused study drug and packaging at each visit, and at the time of study drug discontinuation. The following information will be recorded in the patient's file: dates, quantities, batch numbers, and the unique code numbers assigned to the study products and the patients. The investigators must maintain records documenting that the patients were provided with their respective doses specified in the protocol. Furthermore, they should reconcile all study drugs received from the sponsor. It is the responsibility of the investigator to give reasons for any discrepancies in IMPs accountability

All remaining IMPs, used and unused, shall be collected and returned to the sponsor for destruction at the end of the study.

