6.1.4 Packaging and labelling of the investigational medicinal products

The study products will be packaged and labelled according to current GMP guidelines, good clinical practice (GCP) guidelines, and national legal requirements and instruction will be given in local language. KLS will be responsible for label compliance. Eurofins Gent will be responsible for the packaging, and Eurofins St Gely will be responsible for the labelling and shipping of the IMP and placebo to the investigating sites.

IFB-088 and placebo tablets are packaged in 40 mL high-density polyethylene bottles with polypropylene screw cap lids that contain desiccant. Each bottle contains 65 tablets covering the needs for a bi-daily administration over one month.

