6.4 COMPLIANCE

Patient compliance with study medication will be assessed at each visit and at the time of study products discontinuation by the investigator by direct questioning and by recollection of IMP packaging. Patients will be asked to return all unused study products.

If the time for one visit exceeds the time window, this will be recorded as a deviation from the protocol. Any deviation from the prescribed dosage regimen is to be recorded in the eCRF.

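### Does the compliance formula in SAP 5.2.14 overstate intake by subtracting only the tablets left at V4?

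*SAP*

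**What the plan says.** SAP 5.2.14 takes the number of bottles dispensed times 65 as the tablets dispensed, and twice the days from V0 to V4 as the tablets due. Intake is then: "Number of pills taken = total number of pills dispensed - number of remaining pills at V4". A value is derived only for patients present at V4.

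The protocol sets out the supply in Sections 6.1.2 and 6.1.4: "The patients will receive the IMP at baseline visit (V0: 2 bottles), V2 (2 bottles) and V3 (2 bottles) visits" and "Each bottle contains 65 tablets covering the needs for a bi-daily administration over one month". In Table 2 (Section 3.7) the row "Study drug delivery" is marked at V0, V2 and V3 only.

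Returns are covered in four places:

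- Section 4.1.2, instructions to the patient: "Both used and unused study drug bottles must be returned at the next visit for treatment accountability".
- Section 6.1.3: "Patients will be asked to return all unused study drug and packaging at each visit, and at the time of study drug discontinuation".
- Section 6.4: "Patients will be asked to return all unused study products".
- Section 6.1.3 again, for the end of the study: "All remaining IMPs, used and unused, shall be collected and returned to the sponsor for destruction at the end of the study".

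Neither document says whether tablets brought back before V4 are handed back or kept by the site.

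**The concern.** The formula has one subtraction, at V4, while the return instructions apply at every visit. Even a fully adherent patient arrives at V2 with 74 tablets (130 dispensed, 56 due). If the site kept them, they would appear nowhere in the formula and would be counted as swallowed.

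The compliance percentage is described on the Randomized Set (SAP 5.10). It also supplies the 80% criterion of the per-protocol set (SAP 5.1.4), on which the supportive ALSFRS-R, MITOS and King's College analyses are run (SAP 5.11.2.2.3, 5.11.3.2.2 and 5.11.4.2.2). A formula that counted returned tablets as taken would inflate the table and leave that criterion with almost nothing to screen out.

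**Working it through.** **The plan's own figure.** A month of twice-daily intake is 2 × 30.4375 = 60.9 tablets (month length as in SAP 5.2.13), so a bottle of 65 does cover one month (32.5 days). Six bottles hold 6 × 65 = 390 tablets. Over 26 weeks, 182 × 2 = 364 are due.

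**Supply against need at nominal visit dates** (Protocol 3.1, 3.7, 6.1.2).

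| Interval | Days | Due | Dispensed at start | Difference |
|---|---|---|---|---|
| V0–V2 | 28 | 56 | 130 | +74 |
| V2–V3 | 63 | 126 | 130 | +4 |
| V3–V4 | 91 | 182 | 130 | −52 |
| Total | 182 | 364 | 390 | +26 |

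The last interval can be covered only with tablets left from the first two. The V3–V4 shortfall is 44 to 60 tablets if V4 falls 13 weeks ± 4 days after V3 (Protocol 3.1, 87 to 95 days). It is 36 to 68 if V3 and V4 move separately within the Table 2 windows (83 to 99 days). It never disappears.

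**Reading 1: counted and handed back.** The running stock for full adherence is:

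- V2: 130 − 56 = 74
- V3: 74 + 130 − 126 = 78
- V4: 78 + 130 − 182 = 26

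The SAP score is (390 − 26)/364 = 100%. For a patient taking a fraction p of doses throughout, 390 − 364p tablets remain at V4, so the score is 364p/364 = p. The formula is exact. With V4 on days 178 to 186, the spare stock for full adherence is 390 − 356 = 34 down to 390 − 372 = 18 tablets, so the total supply still suffices.

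**Reading 2: kept by the site at every visit.** The return wording covers V1 and V3bis, where nothing is dispensed. A patient could then take 28 tablets before V1, none until V2, 126 from V2 to V3, 91 from V3 to V3bis, and none afterwards: 28 + 126 + 91 = 245, and 245/364 = 67.3%. Full adherence would be impossible.

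**Reading 3: kept at V2 and V3 but handed back at V1 and V3bis.** Only this mixture produces a misleading score while leaving most of the regimen feasible. The SAP score would be (260 + 182p)/364 for p up to 130/182 = 71.4%. A half-dose taker would score 351/364 = 96.4%. The 80% mark would be passed once p exceeded (291.2 − 260)/182 = 17.1%. No passage describes this practice. It would leave a fully adherent patient 52/2 = 26 days without drug before V4 (18 to 34 days across the Table 2 windows). Protocol 5.3 has patients withdrawn after more than 10 days off treatment, and SAP 5.2.14 scores only those who reach V4.

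**The case for a change.** The strongest case for acting is that bottle quantities show what was intended, not what sites did, and the written instruction was to return drug. If some sites kept leftovers at V2 and V3, a patient taking between 17.1% and (364 − 260)/182 = 57.1% of doses would score between 80% and 100%. Nothing in the score itself would look odd. The 10-day argument does not help there, because such a patient does not run out of tablets.

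Part of this stands. The hand-back is nowhere written, and a retention practice would make the formula wrong for those patients. But the practice must be assumed against the supply plan, and in a selective form. Section 4.1.2 gives accountability as the purpose of the return, which fits bringing bottles back to be counted. Section 6.1.3 separately provides for final collection of all remaining drug at the end of the study, which fits stock staying with the patient until then. Adherent patients running out weeks before V4 would also have exposed retention during conduct.

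The score is not the only check. Compliance is asked about at each visit, dosing deviations go into the eCRF (Protocol 6.4), and non-compliant patients may be withdrawn (Protocol 5.3). Per-protocol exclusions are reviewed before lock (SAP 5.1.4). Quantities are kept in the patient's file (Protocol 6.1.3), so an analyst who learned that tablets had been kept could deduct them.

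Scores just above 100% are not evidence of retention. A morning dose on both the V0 and V4 dates gives 365/364 = 100.3% with no tablet lost or added.

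**Conclusion.** No change to the plan follows. Under the only reading on which the dispensing schedule can be followed as written, the formula returns true compliance at every level of adherence: 364/364 = 100% for full intake, with 26 tablets over. What is missing is a statement that leftovers are counted, handed back and subtracted once, at V4. That is a detail an analyst would fill in the same way from the bottle quantities.

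Taken to mean retention at each visit, the return wording in Protocol 4.1.2, 6.1.3 and 6.4 contradicts the quantities in 6.1.2 and 6.1.4. Those passages must be reconciled; how to do so is the sponsor's decision. It is a matter of accountability wording and alters no planned analysis.

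The conclusion assumes full bottles of 65, visits within their windows, and sites that handed returned tablets back. If the last assumption failed at a site, the effect would be confined to the compliance table and to membership of the per-protocol set. The primary safety analyses and the efficacy analyses on the full analysis set would stand unchanged.
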